### **8.10 Health Economics or Medical Resource Utilization and Health Economics**

Health Economics/Medical Resource Utilization and Health Economics parameters will not be evaluated in this study.

## 9.0 STATISTICAL CONSIDERATIONS

### 9.1 Statistical Hypotheses

This is an exploratory study and no formal hypothesis testing will be performed.

### 9.2 Sample Size Determination

The sample size is not based on statistical power considerations.

Approximately 10 subjects will be enrolled at 8 study centers for study treatment. On Day 1, subjects who meet all of the entry criteria will receive a 750 mg IV dose of ANB019 in an open-label manner followed by 3 doses of 100 mg SC administered on Days 29, 57, and 85.

### 9.3 Populations for Analyses

For purposes of analysis, the analysis sets in Table 3 are defined.

**Table 3 Analysis Sets**

Full Analysis Set (FAS)	The FAS analysis set will include all subjects, regardless of whether or not the treatment was received. Subjects will be analyzed according to treatment received.
Safety Analysis Set	The Safety Analysis Set will include all enrolled subjects who receive at least 1 dose of ANB019. The Safety Analysis Set will be used for all safety analyses. Subjects will be analyzed according to treatment received.
Per Protocol Analysis Set (PPS)	The Per Protocol analysis set will include all subjects in the FAS analysis set who do not have major protocol violations that would affect the evaluation of the primary efficacy endpoint.
PK Analysis Set	The PK analysis set will include all subjects in the Safety Analysis Set who have at least 1 quantifiable PK sample available and who do not have events or deviations with the potential to affect PK concentrations. The PK analysis set will be used for all PK analyses.

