### **5.4 Screen Failures**

Screen failures are defined as subjects who consent to participate in the clinical study but are not subsequently enrolled in the study. A minimal set of screen failure information is required to ensure transparent reporting of screen failure subjects to meet the Consolidated Standards of Reporting Trials publishing requirements and to respond to queries from regulatory authorities. Minimal information includes demography, screen failure details, eligibility criteria, and any SAE.

Individuals who do not meet the criteria for participation in this study (screen failure) may be rescreened once after discussion with Medical Monitor. Rescreened subjects should not be assigned the same subject number as for the initial screening.

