### **7.2 Subject Discontinuation/Withdrawal from the Study**

A subject may withdraw from the study at any time at his/her own request, or may be withdrawn at any time at the discretion of the Investigator for safety, behavioral, compliance, or administrative reasons.

In case of early withdrawal from the study drug and study, the subject will be required to attend the ET visit (see the Schedule of Activities in Section 1.3). Subjects must be withdrawn from the study under the following circumstances, any significant AE which in the opinion of the Investigator is related to the study drug or SAE, or pregnancy occurring through the EOS visit and should be followed-up until outcome:

- Prior to study treatment administration, the Investigator decides that the subject should be withdrawn or is at risk. If this decision is made because of an AE or a clinically significant laboratory value, the study drug should not be administered and appropriate measures are to be taken. AnaptysBio Inc. and/or ██████ is to be notified immediately.
- Significant deviation/lack of compliance with protocol other than the use of excluded/prohibited medications.
- Use of any excluded/prohibited medications that in the opinion of the Investigator necessitates the subject being withdrawn ([Appendix 5](#)).
- Termination of the study by the Investigator or Sponsor.
- Pregnancy ([Appendix 6](#) and Section 8.3.5 Pregnancy).

- New information suggests taking part in the study may not be in the participant's best interest.

If the subject withdraws consent for disclosure of future information, the Sponsor may retain and continue to use any data collected before such a withdrawal of consent.

If a subject withdraws from the study, he/she may request destruction of any samples taken and not tested, and the Investigator must document this in the study center study records.

See Schedule of Activities (Section 1.3) for data to be collected at the time of study discontinuation and follow-up and for any further evaluations that need to be completed.

Subjects withdrawing from the study prematurely for reasons other than a study drug related AE may be replaced at the discretion of the Investigator and Sponsor to ensure the required number of evaluable subjects.

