3.3. EXPLORATORY ENDPOINTS

- Skin biopsy biomarkers (including but not limited to IL-17, IL-23, IL-8, dendritic cells, epidermal thickness, and leukocytes infiltration)
- Changes in serum cytokines as compared to Baseline at Weeks 1, 4, 8, 12, 16, and 24
- Photographic documentation of lesions
- Optional genetic testing (DNA and mRNA)

4. Hypothesis

No formal hypothesis testing will be performed.

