8.1. REFERENCE DATES AND STUDY DAY

Study Day will be calculated from the reference start date and will be used to show start/stop day of assessments and events. The Reference start date (Day 1) is defined as the day of the first dose of study medication and will appear in every listing where an assessment date or event date appears.

If the date of the event is on or after the reference date, then:

Study Day = (date of event – reference date) + 1

If the date of the event is prior to the reference date, then:

Study Day = (date of event – reference date)

In the situation where the event date is partial or missing, Study Day and any corresponding durations will appear partial or missing in the listings.

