11. DISPOSITION AND WITHDRAWALS

All subjects who provided informed consent (ENR) will be accounted for in this study. Subject disposition will be listed and summarized, including:

- Total subjects screened
- Number of screen failures (subjects who consent to participate in the clinical study but are not subsequently entered in the study)
- Total of subjects in the FAS
- Total subjects ongoing (subjects ongoing at the time of the IA)
- Total number of subjects in the SAF
- Total number of subjects in the PPS
- Total number of subjects in the PK Analysis Set
- Total subjects who discontinue from study treatment
- Total subjects who discontinue from the study
- Protocol deviations (PD) as obtained from the CTMS PD log

PDs will be identified and discussed with the Investigator/AnaptysBio in PD review meetings to categorize them, and to finalize analysis set assignment.

A subject is considered to have completed the study if they have completed all scheduled study visits

including the last visit on Day 169.

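### The full analysis set keeps enrolled subjects who never receive ANB019, so each one lowers the single-arm response rate without being able to count as a responder

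*Protocol*

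**What the plan says.** Protocol Table 3 defines the full analysis set (FAS) so that "The FAS analysis set will include all subjects, regardless of whether or not the treatment was received". SAP Table A has the same definition. In both, the next sentence says that subjects are analysed by treatment received. The Safety set in the same tables is limited to enrolled subjects with at least one dose; the FAS has neither limit.

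SAP 17.1.3 runs the primary analysis on the FAS and takes all randomized and enrolled subjects as the denominator at Weeks 4 and 16. SAP 17.2.1.4 uses the same denominator for GPPPGA 0 or 1. Protocol 6.3 says randomization does not apply.

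The time origin is the first dose. SAP 8.1: "The Reference start date (Day 1) is defined as the day of the first dose of study medication". SAP 8.2 anchors baseline to that date, and protocol 9.4 likewise takes the last value before first intake of drug. Under SAP 17.1.2, missing responder status stays missing whatever the reason. The only carry-forward of non-response is for subjects rated non-responders at Week 4. SAP 17.1.4 plans no sensitivity analysis.

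Protocol 7.2 lists this among the reasons for withdrawal: "Prior to study treatment administration, the Investigator decides that the subject should be withdrawn or is at risk". It also lets subjects who withdraw early for reasons other than a drug-related adverse event be replaced.

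**The concern.** Untreated subjects are usually kept in an efficacy set to protect a randomized comparison. This study has none. The primary efficacy objective is the effect of ANB019, and a subject who never received it carries no information on that effect. Under the written rules that subject still counts in practice as a failure, so the reported rate mixes withdrawal before dosing with drug effect.

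If such a subject is replaced, both the subject and the replacement sit in the denominator. No other planned analysis is sure to show the rate in dosed subjects: the per-protocol set is drawn from the FAS and removes only major violations, so a subject withdrawn before dosing without a violation can remain in it. Baseline characteristics are presented on the Safety set (SAP 12), so baseline and efficacy tables could describe different numbers of people. Interim efficacy results may guide protocol changes and later studies (protocol 9.5, SAP 7.2).

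**Working it through.** **The plan's own figure.** Protocol 9.2: "Approximately 10 subjects will be enrolled at 8 study centers for study treatment". It adds: "The sample size is not based on statistical power considerations". No power, alpha or expected response rate is given, so there is no calculation to reproduce; 10 is taken as the planned size.

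**Can an undosed subject be scored?**
1. No first dose means no Day 1 (SAP 8.1), and so no baseline as SAP 8.2 defines it.
2. If baseline mJDA is missing, SAP 17.1.2 falls back on CGI alone. The Schedule of Activities has no CGI before Day 3, so an undosed subject has none to use.
3. Missing status is not imputed, and the Week 4 carry-forward applies only to subjects who were rated. The subject never enters the numerator.
4. The FAS definition and the enrolled denominator keep the subject in the denominator.
5. SAP section 6 lets percentages use subjects with assessments available, where appropriate. The specific rule in 17.1.3 governs the primary endpoint.

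**Size.** The documents give no count of undosed subjects and no expected number of responders; both are assumed here. With d dosed, r responders and u undosed:

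rate = r / (d + u)

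With d = 10 (exact Clopper-Pearson 95% CIs in brackets):

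| Responders r | u = 0 | u = 1 | u = 2 |
|---|---|---|---|
| 6 | 60.0% (26.2 to 87.8) | 54.5% (23.4 to 83.3) | 50.0% (21.1 to 78.9) |
| 7 | 70.0% (34.8 to 93.3) | 63.6% (30.8 to 89.1) | 58.3% (27.7 to 84.8) |
| 8 | 80.0% (44.4 to 97.5) | 72.7% (39.0 to 94.0) | 66.7% (34.9 to 90.1) |
| 10 | 100% (69.2 to 100) | 90.9% (58.7 to 99.8) | 83.3% (51.6 to 97.9) |

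The first undosed subject costs r/10 − r/11 = r/110: 5.5 points for r = 6, 6.4 for r = 7, 7.3 for r = 8 and 9.1 for r = 10.

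If instead 10 is the enrolled total and u of them are undosed, the highest attainable rate is (10 − u)/10: 90% for u = 1 and 80% for u = 2, even if every dosed subject responds.

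**After the fix.** The denominator is d. The u = 0 column applies whatever the number of undosed subjects.

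**The case against.** The strongest reply is that the situation may never arise. Eligibility is rechecked on Day 1 and eligible subjects are dosed that day, so there is little gap between enrolment and dosing. The withdrawal clause in protocol 7.2 does not say before the first dose, and with four dosing visits it may describe someone already dosed. This stands: the plan allows the case, but nothing in it says how often it would occur.

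Safeguards also exist. Set membership is agreed before the interim and final analyses (SAP 8), disposition reports both FAS and Safety totals (SAP 11), denominators must be identifiable (SAP Appendix 1), and all data are listed by subject. With about 10 subjects a reader could recompute the rate. SAP section 4 also says: "No formal hypothesis testing will be performed". This limits the harm, but the membership review must apply the definition as written, and that definition retains the undosed.

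The rule can be called conservative. In a single arm, though, it measures something other than response to the drug.

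It is also true that an undosed subject may have screening mJDA and GPPPGA values. Baseline is absent by the SAP's definition; a pre-dose measurement may well exist.

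A reader might go further and infer that screen failures enter the FAS, because SAP 11 says "All subjects who provided informed consent (ENR) will be accounted for in this study" and the abbreviation suggests enrolled. The documents do not support that. SAP 11 counts screen failures and FAS subjects on separate lines. The abbreviation appears in neither the FAS definition nor the 17.1.3 denominator. Protocol 5.4 settles the term: "Screen failures are defined as subjects who consent to participate in the clinical study but are not subsequently enrolled in the study". The label needs at most a wording clean-up.

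**Conclusion.** The point holds for enrolled subjects who are never dosed, and only for them. The FAS definition contradicts itself in a one-arm study, and together with the denominator in SAP 17.1.3 and 17.2.1.4 it counts such subjects against the drug.

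The dilution is conditional. It is zero if every enrolled subject receives a dose. With 10 dosed subjects, one undosed subject lowers the rate by about 5 to 9 percentage points over the cases shown; with 7 responders it falls from 70% to 64%, and to 58% with two. These shifts are small beside the width of the confidence intervals, but they are one-directional and have nothing to do with ANB019. The numbers of responders and of undosed subjects are assumptions.

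**What to change.** - In protocol Table 3 and SAP Table A, define the FAS as all enrolled subjects who receive at least one dose of ANB019, in whole or in part.
- In SAP 17.1.3 and 17.2.1.4, use that set as the denominator and delete the word randomized.
- Use enrolled in the sense of protocol 5.4 throughout, and correct the label in SAP 11.
- Show subjects enrolled but not dosed in disposition only.

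The cost is wording. FAS membership becomes the same as the Safety set. Because Table 3 is protocol text, the change needs a protocol amendment or, if made in the SAP alone, an entry in SAP 5.4, which now declares no departures from the protocol.

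This does not settle how dosed subjects with missing responder status are counted. SAP 17.1.2 leaves them missing while 17.1.3 keeps them in the denominator, so the SAP needs a separate, explicit rule for them.

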### 9.4 Statistical Analyses

The statistical analysis will be performed using statistical analysis system (SAS®) Version 9.4 or higher if available. All details regarding the statistical analysis and the preparation of tables,

listings and figures will be described in the statistical analysis plan (SAP). The SAP will be developed and finalized before database lock and will describe the subject analysis sets to be included in the analyses, and procedures for accounting for missing, unused, and spurious data. This section is a summary of the planned statistical analyses of the primary and secondary endpoints.

The default summary statistics for continuous variables includes number of contributing observations (n), mean, standard deviation (SD), median, minimum, and maximum. (See Section 9.4.7 for PK).

For categorical variables, the number and percentage (the percentage of subjects in each category relative to the total number of subjects in the relevant analysis set or relative to the total number of subjects in the relevant analysis set, with assessments available [where appropriate]) in each category will be the default summary presentation.

Unless otherwise specified, “baseline” is defined as the last observed value of the parameter of interest prior to the first intake of study drug (this includes unscheduled visits). For numerical variables, change from Baseline will be calculated as the difference between the value of interest and the corresponding baseline value.

Point estimates will be accompanied with 2-sided 95% confidence interval (CIs), where applicable.

In the case of normality assumption violations, appropriate non-parametric methods will be used for analysis.

All data will be presented in by subject listings.

#### **9.4.1 Subject Disposition**

A tabular presentation of the subject disposition will be provided. It will include the number of subjects screened, enrolled, treated, completed as well as the number of dropouts, with reasons for discontinuation, and major protocol deviations or violations.

A listing will be presented to describe dates of screening, assigned treatment, screen failed with reason, completion or early withdrawal, and the reason for early discontinuation, if applicable, for each subject. A list of protocol deviations/violations will be identified and discussed with the Investigator/AnaptysBio Inc. in dry-run to categorize as major or minor and the same will be reported.

#### **9.4.2 Subject Characteristics and Medical History**

Subject characteristics obtained at Screening will be summarized for all subjects taking ANB019. Subject characteristics may include, but are not limited to age, gender, height, weight, and BMI.

Summaries will include descriptive statistics for continuous variables (sample size [n], mean, SD, median, minimum, and maximum) and for categorical variables (sample size, frequency, and percent).

Medical history will be coded using the Medical Dictionary for Regulatory Activities (MedDRA) dictionary latest version and listed for all subjects.

#### **9.4.3 Concomitant Medication**

All medications will be coded using the World Health Organization Drug Dictionary and Anatomical Therapeutic Chemical (ATC) system. Each medication will be classified as prior medication if it is stopped prior to the first dose of study drug, or as concomitant medication if it is ongoing at the time of the first dose or is started after the first dose of study drug. Prior, concomitant and rescue medications will be summarized by ATC level 2 categories and preferred name.

A listing of prior, concomitant, and rescue medications will be presented.

#### **9.4.4 Efficacy Analyses**

##### ***9.4.4.1 Analysis of Primary Efficacy Endpoints***

The primary efficacy endpoint is the proportion of subjects achieving clinical response at Weeks 4 and 16. Clinical response is defined as “Very much improved”, “Much improved”, and “Minimally improved” on CGI scale according to modified JDA severity index total score. The number and percentage of subjects achieving clinical response will be summarized in tabular form at Weeks 4 and 16. Each subjects CGI score will be plotted at all study visits.

##### ***9.4.4.2 Analysis of Secondary Efficacy Endpoints***

Following are the secondary efficacy endpoints:

- Change in modified JDA severity index total skin lesions score (sum of erythema, erythema with pustules, edema) at all study visits.

Descriptive statistics will be presented at all study visits. Each subject’s modified JDA severity index total skin lesion score will be plotted at all study visits.

- Change in affected BSA of erythema with pustules, erythema, and edema as measured by modified JDA severity index score at all study visits:

Descriptive statistics will be generated at all study visits. An overlay plot of each subject’s value over all study visits will be generated for each component score.

- Change in total and individual scores in systemic manifestations and laboratory findings as measured by modified JDA severity index at all study visits.

Descriptive statistics will be generated at each measurement time for each numeric systemic manifestation and laboratory finding. An overlay plot of each subject's value over all study visits will be generated for each measurement time.

- GPPPGA change from Baseline scores for all study visits.
- GPPPGA score at all study visits.

The GPPPGA will be summarized at each postbaseline visit for change from Baseline scores and for the proportion of subjects achieving a GPPPGA score of 0 or 1. A separate overlay plot will display each subject's GPPPGA score for all study visits.

- Change in PASI score to evaluate a subject's overall PP disease state if present for all study visits:

Summary statistics will be provided for absolute PASI scores as well as for percent change from Baseline for all study visits.

- Change in DLQI total score at all study visits:

Summary statistics will be provided for average DLQI scores, as well as for percent change from Baseline for all study visits.

#### **9.4.5 Safety Analyses**

- Assessment of AEs/SAEs (potentially significant and clinically important AEs, SAEs, and AEs leading to withdrawal)
- Physical examinations
- 12-lead ECG
- Vital signs
- Clinical safety laboratory tests (hematology, biochemistry, and urinalysis).

All safety analyses will be performed on the Safety Analysis Set.

##### **9.4.5.1 Adverse Events and Serious Adverse Events**

Treatment-emergent adverse event: A TEAE is defined as:

- A new event that occurs during or after first dose of study treatment or,
- Any event present at baseline that worsens in either intensity or frequency after first dose of study treatment.

Only TEAEs will be summarized.

Adverse events will be coded using the MedDRA. Number of events and percentage will be tabulated by preferred term and system organ class. An event that occurred one or more times on treatment period for a subject will contribute 1 observation to the numerator and denominator

comprising all safety subjects exposed to ANB019. If the intensity or seriousness of the AE changes, the overall intensity or seriousness will be the maximum intensity or seriousness of the multiple occurrences. The TEAEs, AESIs, SAEs, TEAEs leading to treatment discontinuation, and TEAEs leading to withdrawal of subject will be tabulated for each treatment period.

Adverse events, AESIs, and SAEs will be listed for each subject.

Summaries over SOC, PT and listings of TEAEs, TEAEs leading to death, SAEs, potentially significant TEAEs, clinically important TEAEs, and TEAEs that led to discontinuation from the study or of the study drug will be presented. Summaries will also be presented by relatedness to the study drug and the severity of the TEAE.

#### **9.4.5.2 *Physical Examinations, 12-Lead ECG, Vital Signs and Clinical Safety Laboratory Tests (Hematology, Biochemistry, and Urinalysis)***

Summaries and listings of data for both limited and complete physical examination findings, vital signs, hematology, biochemistry, and urinalysis laboratory tests will be presented. Appropriate descriptive statistics will be summarized for the observed value at each scheduled assessment and for the corresponding change from Baseline.

For hematology and biochemistry tests, listings of subject data will also flag up any abnormal or out-of-range values. Clinically significant changes in the laboratory test parameters will be summarized and listed. Hematology and clinical laboratory data will be reported in System International units.

Descriptive statistics will be used to present the safety outcomes including, physical examination results, weight, BMI, 12-lead ECG, vital signs measurements, and clinical laboratory test results.

Change from Baseline will also be summarized for vital signs measurements, clinical laboratory test results.

All ECG data results (normal/abnormal) will be summarized using frequency and percentages. Clinically significant abnormalities will be presented in by subject listings.

